5.1.3 Treatment Period (Substudy 1 and Substudy 2)

Substudy 1 – Treatment Intensification (TI) Period

There is one treatment group for this study. After meeting entry criteria, subjects will receive ABT-450/r 200/100 mg, ABT-267 25 mg, pegIFN and RBV. ABT-450/r and ABT-267 will be administered once daily; pegIFN will be dosed once weekly and RBV will be dosed twice daily. See Section 5.5.1 for details.

At the TI Day 1 Visit, subjects will undergo the study procedures identified in [Table 5](#) (and [Table 6](#) for cirrhotic subjects).

Subjects will be administered study drugs at the site on TI Day 1. Plasma and serum samples for pharmacokinetic analysis will be collected at TI Week 1 through TI Week 24 (Substudy 1). All subjects will continue to return to the site on an outpatient basis through TI Week 24 for the study procedures identified in [Table 5](#) (and [Table 6](#) for cirrhotic subjects). Sites should ensure that subjects adhere to the study visits listed in [Table 5](#) (and [Table 6](#) for cirrhotic subjects). Subjects who cannot complete their study visit per the visit schedule through TI Week 24 should ensure they do not run out of study drug prior to their next study visit. Compliance is critical to ensure adequate drug exposure. Some of the Treatment Period study visits and visit activities (including but not limited to vital signs, clinical laboratory tests and concomitant medication assessment) may be conducted in the home or non-hospital/clinic environment by qualified individuals at the request of the investigator and with the agreement of the subject.

Subjects who prematurely discontinue from the DAA study drug treatment in Substudy 1 should return for a TI Week 24/TI Discontinuation Visit and undergo study procedures as defined in [Table 5](#) (and [Table 6](#) for cirrhotic subjects) and as described in Section 5.4.1. The subject should either proceed to Substudy 2 if the investigator feels it is appropriate or proceed to Substudy 3 if it is not appropriate to continue on Substudy 2. Refer to [Figure 3](#), Subject Flow Chart.

Substudy 2 – PegIFN/RBV (PR) Treatment Period

Subjects who complete TI treatment will continue on to Substudy 2, the PR Treatment Period, for continued dosing of pegIFN and RBV. Subjects who prematurely discontinue TI treatment may also continue on to Substudy 2, unless the investigator feels it is not appropriate to continue pegIFN and RBV either due to toxicity or to lack of virologic response. Substudy 2 will begin the day after the last dose of DAA. Substudy 2 is designed to allow completion of pegIFN + RBV treatment for a total duration of 48 weeks across Substudies 1 and 2 and to monitor HCV RNA levels and emergence of any ABT-450 and ABT-267 resistance-associated variants.

For subjects who complete Substudy 1, an additional 24 weeks of pegIFN and RBV will be administered in Substudy 2. Subjects who complete 24 weeks of treatment in Substudy 2 should undergo the procedures listed in the PR Final/PR Discontinuation Visit in [Table 5](#) (and [Table 6](#) for cirrhotic subjects), not the PR Week 24 visit and then continue on to Substudy 3.

Subjects who receive less than 24 weeks of TI treatment in Substudy 1 may receive pegIFN and RBV in Substudy 2 at the discretion of the investigator, up to a total of 48 weeks across Substudies 1 and 2. All subjects will continue to return to the site on an outpatient basis for the PR Treatment study procedures identified in [Table 5](#) (and [Table 6](#) for cirrhotic subjects). For those subjects who do not complete 24 weeks of TI treatment in Substudy 1, additional study visits as indicated in [Table 5](#) (and [Table 6](#) for cirrhotic subjects) should be performed if required to complete a total of 48 weeks across Substudies 1 and 2. These additional visits are PR Week 24, PR Week 36 and PR

Final/PR Discontinuation Visit (which may be out to 48 weeks or earlier). All subjects should complete the PR Final/PR Discontinuation Visit procedures at that subject's final visit in Substudy 2. In some cases this final visit may fall in between study visits listed in [Table 5](#). Sites should ensure that subjects adhere to the study visits listed in [Table 5](#) (and [Table 6](#) for cirrhotic subjects). Subjects who cannot complete their study visit per the visit schedule should ensure they do not run out of study drug prior to their next study visit. Compliance is critical to ensure adequate drug exposure.

Subjects who prematurely discontinue Substudy 2 should return to the site for a PR Final/PR Discontinuation Visit as outlined in [Table 5](#) (and [Table 6](#) for cirrhotic subjects).

Safety and tolerability of the treatments will be assessed throughout the study. Laboratory testing will include chemistry, hematology, and urinalysis (refer to [Table 9](#)). Ongoing review of the data is planned in order to determine if subjects meet the virologic stopping criteria.

Ongoing review of the data is also planned for non-efficacy (futility) assessment. Data will be assessed separately for the population of subjects who were null or partial responders to prior pegIFN/RBV treatment or experienced any prior failure with pegIFN/RBV plus telaprevir in the previous AbbVie/Abbott study, and for the population of subjects who do not fall in the previous population at the time of enrollment into this study. Refer to Section [5.4.2](#) for further details regarding these ongoing reviews.

5.1.4 Post-Treatment Follow-Up Period (Substudy 3)

In Substudy 3, the Post-treatment (PT) Period, subjects will be followed for 48 weeks after the last dose of study drugs for evaluation of the emergence, evolution and persistence of viral resistance to ABT-450/r and ABT-267 and for viral response.

[figure not shown]
All subjects who receive at least 1 dose of DAA will be monitored for viral resistance on an outpatient basis for an additional 48 weeks following the last dose of study drugs, regardless of whether they prematurely discontinue study drug treatment or complete treatment as planned in Substudies 1 and 2. Refer to [Figure 3](#), Subject Flow Chart.

Subjects will return to the study site as outlined in [Table 7](#) (and [Table 8](#) for cirrhotic subjects) for post-treatment visit procedures including resistance monitoring, HCV RNA testing, and assessment of adverse events (for 30 days post-treatment only) and serious adverse events. Substudy 3 will begin the day after the last dose of study drug treatment. Subjects who prematurely discontinue Substudy 3 should return to the site for a PT Week 48/PT Discontinuation Visit as outlined in [Table 7](#) (and [Table 8](#) for cirrhotic subjects).

Some of the Post-Treatment Period study visits and visit activities (including but not limited to vital signs, clinical laboratory tests and concomitant medication assessment) may be conducted in the home or non-hospital/clinic environment at the request of the Investigator and with the agreement of the subject.

All subjects who receive at least one dose of DAA may be offered participation in a separate AbbVie-sponsored observational study to evaluate the durability of virologic response for subjects who achieve SVR or to study the emergence and persistence of resistant variants in subjects who fail treatment.

Figure 3. Subject Flow Chart

5.2 Selection of Study Population

Subjects who have experienced virologic failure in a previous AbbVie/Abbott DAA combination study and who meet the inclusion criteria, and who do not meet any of the exclusion criteria, will be eligible for enrollment into the study. In addition, no more than ten (10) subjects who received pegIFN/RBV plus telaprevir in a previous AbbVie/Abbott study will be enrolled.

5.2.1 Inclusion Criteria

Subjects must meet all of the following inclusion criteria:

1. Must voluntarily sign and date an informed consent, approved by an Institutional Review Board/Ethics Committee (IRB/EC), prior to the initiation of any study specific procedure.
2. Subject must be able to understand and adhere to the study visit schedule and all other protocol requirements.
3. Subject must have experienced virologic failure as defined in a previous AbbVie/Abbott DAA combination study.
4. Female who is:
 - not of childbearing potential, defined as:
 - postmenopausal for at least 2 years prior to screening (defined as amenorrheic for longer than 2 years, age appropriate, and confirmed by a follicle-stimulating hormone [FSH] level indicating a postmenopausal state), or
 - surgically sterile (defined as bilateral tubal ligation, bilateral oophorectomy or hysterectomy) or has a vasectomized partner(s), or
 - practicing total abstinence from sexual intercourse (minimum 1 complete menstrual cycle), or
 - sexually active with female partners only
 - of childbearing potential and sexually active with male partner(s):
 - currently using at least one effective method of birth control at the time of screening and agree to practice two effective methods of birth control while receiving study drugs (as outlined in the subject information and consent form or other subject information documents), starting with Study Day 1 and for 7 months after stopping study drug or as directed by the local ribavirin label (Estrogen-containing hormonal contraceptives, including oral, injectable, implantable, patch and ring varieties, may not be used during DAA treatment).

5. Females must have negative results for pregnancy tests performed:
 - at Screening by urine specimen within 42 days prior to initial study drug administration, and
 - at Baseline (prior to dosing) by urine specimen.Female subjects with a borderline hCG result at Day 1 may enroll into the study if they either:
 - have a documented history of bilateral tubal ligation, hysterectomy, bilateral oophorectomy; or
 - are confirmed to be postmenopausal defined as amenorrheic for longer than 2 years, age appropriate, and confirmed by a follicle-stimulating hormone (FSH) level indicating a postmenopausal state at Screening.
6. Sexually active males must be surgically sterile or have male partners only or if sexually active with female partner(s) of childbearing potential must agree to practice two effective forms of birth control (as outlined in the subject information and consent form or other subject information documents) throughout the course of the study, starting with Study Day 1 and for 7 months after stopping study drug or as directed by the local ribavirin label. (Note: Contraceptives containing ethinyl estradiol are considered effective if used by the female partners of male subjects.)
7. Subject must be considered an appropriate candidate for pegIFN, RBV, ABT-450/r and ABT-267 therapy in the opinion of the investigator.
8. Subject is infected with HCV genotype 1 at the Screening Visit.
9. Subject has a plasma HCV RNA level $\geq 2,000$ International Units (IU)/mL at the Pre-screening Visit.

In addition to Inclusion Criteria 1 through 9, subjects diagnosed with cirrhosis must also meet the following criteria:

10. Compensated cirrhosis defined as Child-Pugh score of ≤ 6 at Screening.

11. Absence of hepatocellular carcinoma (HCC) based on a negative ultrasound, computed tomography (CT) scan or magnetic resonance imaging (MRI) performed within 3 months prior to Screening or during the Screening period.

Rationale for Inclusion Criteria

- (1, 2) In accordance with harmonized Good Clinical Practice (GCP).
- (3 – 7) For safety of the subjects.
- (8 – 11) To select the appropriate subject population.

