
In Substudy 3, the study will monitor and evaluate subjects for 48 weeks after the last dose of study drug for HCV RNA and the evolution and persistence of viral resistance to DAAs.

Study Procedures:

Subjects will visit the site on an outpatient basis for testing of HCV RNA, pharmacokinetics sampling, safety and resistance. Safety of the treatments will be evaluated throughout the study using assessments of adverse events (AEs), physical exam findings, electrocardiograms (ECGs), and laboratory parameters which will include chemistry, hematology and urinalysis. Additional procedures will be done for cirrhotic subjects to evaluate hepatic compensation and to rule-out hepatocellular carcinoma.

Diagnosis and Main Criteria for Inclusion/Exclusion:

Main Inclusion:

To be enrolled in this protocol, subjects must meet all of the following inclusion criteria:

1. Subject must have experienced virologic failure as defined in a previous AbbVie/Abbott DAA combination trial.
2. Female subjects of childbearing potential must be willing to use two effective forms of birth control (not including contraceptives containing ethinyl estradiol) while receiving study drug and for 7 months (or per local ribavirin label) after stopping study drug (Note: Estrogen-containing hormonal contraceptives, including oral, injectable, implantable, patch and ring varieties, may not be used during DAA treatment). Females are considered of childbearing potential unless they are either:
 - Post-menopausal for at least 2 years prior to screening (defined as amenorrheic for longer than 2 years, age appropriate, and confirmed by a follicle-stimulating hormone [FSH] level indicating a postmenopausal state), or
 - Surgically sterile (defined as history of bilateral tubal ligation, bilateral oophorectomy or hysterectomy) or has a vasectomized partner(s), or
 - Practicing total abstinence from sexual intercourse (minimum 1 complete menstrual cycle), or
 - Sexually active with female partner(s) only.

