- These visits are only needed for subjects who did not complete 24 weeks of pegIFN/RBV in Substudy 1 such that the subject completes a total of 48 weeks of pegIFN/RBV across Substudy 1 and Substudy 2.
- Subjects who prematurely discontinue from the pegIFN/RBV study drug treatment in Substudy 2 should return for a PR Final/PR Discontinuation Visit. These subjects will continue on to Substudy 3.

Table 5. Study Activities (Continued)

- f. Where applicable/locally available.
- g. The subject's medical history will be updated at the Screening Visit with any relevant information that was not collected in the previous AbbVie/Abbott DAA combination study and any new medical history that occurred between the end of the previous AbbVie/Abbott DAA combination study and this study. The subject's medical history will also be updated if needed for the period between the Screening Visit and the TI Day 1 Visit.
- h. Only concomitant medications related to HCV treatment and/or medications prescribed in association with a serious adverse event will be collected during Substudy 2.
- i. Height will be measured at Screening only. Will include a thorough eye exam to confirm that the subject is an appropriate candidate for pegIFN therapy.
- j. Urine pregnancy testing is not required after the TI Day 1 Visit for female subjects with a documented prior hysterectomy or bilateral oophorectomy or bilateral tubal ligation or those confirmed to be postmenopausal. Urine pregnancy tests must be conducted monthly during treatment in Substudy 1 and Substudy 2 (per local RBV label) for women of childbearing potential. Subjects may come to the clinic for an unscheduled visit for pregnancy testing at PR Study Weeks 16 and 20 and PR Weeks 28, 32, 40 and 44 if needed or perform the tests at home with test kits provided by the site. Sites may substitute serum pregnancy testing for urine pregnancy testing only if required per local regulations.
- k. Refer to Section 5.5.1 for additional information on treatments administered and Section 5.5.8 for additional information on drug accountability. Drug Accountability is not assessed at TI Day 1.
- l. Collected from subjects participating in study under original protocol and Amendments 1 – 9.
- m. MEMS cap is collected at any point upon completion of Substudy 1.

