When an ECG is scheduled on the same day as a blood collection, the ECG will be obtained prior to the blood collection.

ECGs will be recorded after the subject has been supine for at least 5 minutes. Subjects should be instructed to remain completely stationary during the ECG recording (approximately 10 seconds), with no talking, laughing, deep breathing, sleeping, or swallowing.

The ECGs will be evaluated by an appropriately trained physician at the site ("local reader"). The local reader from the site will interpret, sign, and date all ECG tracings and will provide his/her global interpretation as a written comment on the tracing using the following categories:

- Normal ECG
- Abnormal ECG – not clinically significant
- Abnormal ECG – clinically significant

The local reader will capture the assessment of the ECG tracing in the subject's source notes. Only the local reader's assessment of the ECG tracing will be collected on case report forms, entered into the database and summarized.

Pregnancy Test

A serum pregnancy test will be performed at TI Day 1 for all female subjects and analyzed by the central laboratory. In addition, a urine pregnancy test will be performed for female subjects at the visits specified in [Table 5](#) and [Table 7](#). All urine pregnancy tests will be performed on-site during the study visit, if there is a scheduled visit. Urine pregnancy tests are not required after TI Day 1 for female subjects with a documented prior hysterectomy or bilateral tubal ligation or bilateral oophorectomy or who are confirmed to be postmenopausal. Confirmation of postmenopausal status will be determined based on the subject's history and the FSH level obtained at the Screening Visit. Sites may substitute serum pregnancy testing for urine pregnancy testing only if required per local regulations.

Women of childbearing potential should have urine pregnancy testing completed monthly during treatment with RBV and monthly for 7 months after the discontinuation of RBV or according to the local RBV label and/or local treatment guidelines for RBV. During the PR Treatment Period and the PT Period where there is not a scheduled study visit (i.e., PR Weeks 16 and 20, 28, 32, 40 and 44, and PT Week 16, 20 and 28), female subjects of childbearing potential may either have pregnancy testing performed at the site as an

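### Inclusion 4 labels some fertile women 'not of childbearing potential'; read literally with the pregnancy-testing rules, the label could drop PR Weeks 16 and 20 and leave 12 weeks between tests on RBV instead of 4

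*Protocol*

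**What the plan says.** **Definition.** Inclusion 4 (Protocol 5.2.1) lists who is not of childbearing potential. Besides menopause, the list has "surgically sterile (defined as bilateral tubal ligation, bilateral oophorectomy or hysterectomy) or has a vasectomized partner(s), or" and "practicing total abstinence from sexual intercourse (minimum 1 complete menstrual cycle), or" women with female partners only. Synopsis Inclusion 2 gives the same categories under "Females are considered of childbearing potential unless they are either". The protocol has no other express definition of the term.

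**Waiver.** Table 5 note j says "Urine pregnancy testing is not required after the TI Day 1 Visit for female subjects with a documented prior hysterectomy or bilateral oophorectomy", and goes on to add bilateral tubal ligation and confirmed menopause. Section 5.3.1.1 and Table 9 note b use the same list. It is purely physiological.

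**Tests at visits.** Section 5.3.1.1 states that "a urine pregnancy test will be performed for female subjects at the visits specified in" Tables 5 and 7, with no limit to childbearing potential.

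**Monthly duty.** Note j: "Urine pregnancy tests must be conducted monthly during treatment in Substudy 1 and Substudy 2 (per local RBV label) for women of childbearing potential". Section 5.3.1.1 has a matching sentence.

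**Tests between visits.** Section 5.3.1.1 covers the weeks "where there is not a scheduled study visit (i.e., PR Weeks 16 and 20, 28, 32, 40 and 44" and certain post-treatment weeks), and offers a site or home test to female subjects of childbearing potential. Note j covers the same on-treatment weeks with a broader subject: "Subjects may come to the clinic for an unscheduled visit for pregnancy testing at PR Study Weeks 16 and 20" and the later PR weeks.

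**The concern.** The testing rules leave a group in between. A woman who is abstinent, has a vasectomized partner or has only female partners is fertile. She is not on the waiver list, so she is tested at visits. But the protocol's own definition places her outside the monthly duty, and outside the between-visit tests as 5.3.1.1 words them. Two sites with the same text could test the same woman every 4 weeks or only at scheduled visits.

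What is at stake is fetal exposure to RBV. Sections 5.4.1 and 6.6 differ on the other drugs after a positive pregnancy test, but both require RBV to stop at once. The interval between tests therefore limits how long an undetected pregnancy stays exposed.

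**Working it through.** **Inputs**
- Visits (Table 5): TI Weeks 1, 2, 4, 8, 12, 16, 20, 24; PR Weeks 2, 4, 8, 12; PR Weeks 24 and 36 only for subjects who did not complete Substudy 1; PR Final.
- Completers of Substudy 2 do PR Final in place of PR Week 24 (5.1.3).
- PR Weeks 16, 20, 28, 32, 40 and 44 have no visit (5.3.1.1).
- pegIFN/RBV lasts up to 48 weeks in total across Substudies 1 and 2 (5.1.3).
- 'Monthly' is taken as every 4 weeks.

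**The plan's own interval.** With PR Weeks 16 and 20 included, the late tests fall at PR 12, 16, 20 and 24. Each gap is 4 weeks. No gap earlier in treatment exceeds 4 weeks either, so the monthly rule is met.

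**Visit-only testing, 24 + 24 weeks**
- PR Week 12 to PR Final: 24 − 12 = 12 weeks.
- SAP Table 2 agrees: nominal days 84 and 168 with nothing between, and (168 − 84)/7 = 12 weeks.
- Excess over the monthly rule: 12 − 4 = 8 weeks.
- Tests omitted: PR 16 and PR 20 = 2.

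The 12-week gap holds even if Table 5 marks a test at every visit, because there is no visit in between.

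**Visit-only testing after an early DAA stop.** Section 5.4.1.1 allows a subject who fails the TI Week 4 criterion to stop DAAs and continue pegIFN/RBV at the investigator's discretion.
- The PR period then runs to about 48 − 4 = 44 weeks.
- Visits from PR 12 on: 12, 24, 36, Final (44).
- Gaps: 24 − 12 = 12; 36 − 24 = 12; 44 − 36 = 8 weeks.
- Tests omitted: PR 16, 20, 28, 32 and 40 = 5.
- PR 44 becomes a between-visit week only if DAAs stop before TI Week 4.

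**Share of four-weekly points.** This assumes a urine test at each treatment visit, because the pregnancy row of Table 5 is not legible in the text available.
- 24 + 24 weeks: 6 points in TI and 6 in PR = 12; 2/12 = 17%.
- DAA stop at TI Week 4: TI 4 plus PR 4 to 44 in steps of 4 = 1 + 11 = 12; 5/12 = 42%.

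The interval is the firmer measure; these shares depend on the assumption.

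**The case against.** The strongest reply is that the testing text already points to the safer reading. Wherever the protocol waives a test or interprets a result, it uses the physiological list: note j, 5.3.1.1, Table 9 note b, and Inclusion 5 for borderline hCG results. The behavioural categories appear only inside the contraception criteria, and the second branch of Inclusion 4 treats childbearing potential and sexual activity with men as separate matters. Note j offers the between-visit tests to subjects without restriction. Both monthly-testing passages also refer to the local RBV label, which may require monthly tests anyway. All of this stands, and it makes the unsafe reading less likely. But none of it says which reading governs, and the literal reading only applies the protocol's definition to the protocol's own term.

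A second reply is that the labels describe current behaviour. A woman who begins sex with a fertile man no longer meets the label, and monthly testing then applies. This also stands. It reduces the residual risk mainly to vasectomy failure or an undisclosed change of behaviour.

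A reader might go further and infer that the protocol exempts these women from pregnancy testing altogether. It does not: they are not on the waiver list, and visit-based tests apply to female subjects generally. Nor do the documents show that any test was missed. Post-treatment testing is a separate matter, because Table 7 note c refers additional tests to the local label, guidelines or legal requirements.

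A reader might also want to align the two-method contraception sentence in 5.3.1.1, which exempts only the surgically sterile, with the wider exemptions of Inclusion 4. That would loosen contraception for a fertile woman on RBV. It would also leave the unrestricted two-method sentences in 5.1.2 and 5.2.3.2 inconsistent with it.

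**Conclusion.** The point holds as a minor subject-safety clarification. A stated definition, applied literally, lengthens the interval between tests on RBV from 4 to 12 weeks for fertile women outside the waiver list, with a further 12-week gap if pegIFN/RBV is extended after a DAA stop at TI Week 4. The 8 extra weeks of possible undetected exposure are an upper bound: they require a conception in these groups soon after PR Week 12 and ignore symptoms or a missed period.

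The conclusion assumes a site that carries the Inclusion 4 label into the testing rules and a local RBV label that does not close the gap. The documents do not give the content of that label, the frequency of early DAA stops or the number of affected women. With enrollment of up to 35, that number is probably small and could be zero. No endpoint or analysis is affected.

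**What to change.** - In Table 5 note j and in 5.3.1.1, for the on-treatment monthly and between-visit tests, replace 'women of childbearing potential' and 'female subjects of childbearing potential' with: all female subjects except those with documented hysterectomy, bilateral oophorectomy, bilateral tubal ligation or FSH-confirmed menopause.
- In Inclusion 4 and Synopsis Inclusion 2, state that abstinence, a vasectomized partner and female partners only serve solely to set the contraception requirement.
- Leave the two-method contraception sentence in 5.3.1.1 as it is.

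The change is wording only. The cost is about 2 extra urine tests per affected woman, or about 5 if DAAs stop at TI Week 4, done at home or on site as 5.3.1.1 already allows. If 0 to 5 women were affected (an assumption), that is 0 to 5 × 2 = 10 tests in the whole study, or 0 to 5 × 5 = 25 if all of them stopped DAAs at TI Week 4.
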